Prevalence of Gastroesophageal Reflux Disease, Its Association With Eating Behavior and Psychological Disturbance, and Its Impact On Quality Of Life, Among Medical Students In The MENA Region, A Multinational Cross-Sectional Study

NCT registration: Not yet registered

Document data: 5 August 2025

Introduction

Gastroesophageal reflux disease (GERD) is a common gastrointestinal disease. It is a chronic condition that is characterized by the regurgitation of stomach contents into the esophagus and is associated with heartburn. The occurrence of these symptoms for at least two weeks increases the likelihood of having GERD. Other GERD symptoms include chest pain, nausea, dysphagia, burping, water brash, and vomiting(Argyrou et al., 2018; Richter & Rubenstein, 2018). All these symptoms negatively affect the patients' quality of life. The pathophysiology of GERD is multifactorial(Lee & McColl, 2013). Several factors have been suggested to cause GERD, including a hypotensive lower esophageal sphincter (LOS) and a defect in the gastric sling/clasp muscle fiber component(Hershcovici et al., 2011; Orlando, 2001).

The global prevalence of GERD is about 13.98%(Nirwan et al., 2020) with variation among different countries and ethnic groups. In East Asia, it ranges from 2.5% to 7.5%, 8.5 to 25.9% in Europe, 18.1% to 27.8% in South and North America, and about 11.6% in Australia. In the Middle East, it ranges from 8.7% to 33.1%(El-Serag et al., 2014).

Several risk factors have been identified that increase the likelihood of having GERD. Obesity was found to be one of the risk factors that increases GERD. Also, dietary habits such as spicy food, coffee drinks, or administering NSAIDs increase the prevalence of having GERD(Jarosz & Taraszewska, 2014).

On the other hand, psychological factors also play an important role in GERD severity. Both stress and anxiety are linked to an increase in GERD. A previous study showed that stress can increase heartburn symptoms in patients with heartburn(He et al., 2022) and also increase in anxiety level was associated with an increase in esophageal reflux(Song et al., 2013). Finally, depression was found to be associated with GERD, which can be explained by a change in the eating behavior in depressed patients(Mohammad et al., 2019).

Rationale

Medical students suffer from a study burden, which increases their level of anxiety and stress. They also have a higher likelihood of having trouble with eating behavior or having a lot

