of coffee daily. This increases their likelihood of having GERD. In the Middle East, fewer studies have assessed the effect of GERD. A recent cross-sectional study assessed the prevalence of GERD among medical students in Egypt. They found a prevalence of 17.1%. They found an association between increasing stress levels and increasing GERD severity. Also, smoking was a significant risk factor for GERD symptoms. Another cross-sectional study among medical students in 21 universities in Egypt. They reported a prevalence of 28.4%. Again, they found that an increasing level of stress and anxiety was associated with increasing GERD severity. Finally, Two cross-sectional studies were conducted in Saudi Arabia. They reported a prevalence of 23.8% and 23.1% respectively. To our knowledge, no study has assessed the GERD and its related quality of life among medical students in Middle East and linked their findings with eating behaviour

Research Questions

1. What is the prevalence of GERD among medical students and interns, its risk factors, its impact on health-related quality of life, and psychological disturbance?
2. What is the impact of eating behavior on GERD prevalence?

Aim

To improve the quality of life among medical students and interns in the Middle East countries

Objectives

1. To assess the prevalence of GERD among medical students and interns in the Middle East
2. To assess the effect of GERD on health-related quality of life
3. To assess the associated risk factors of GERD
4. To assess the impact of eating behavior on GERD prevalence
5. To assess the impact of stress, anxiety, and depression on increasing GERD prevalence

Methodology

Technical design

1. **Study design:** Cross-sectional study

2. **Setting:** Medical students in some Middle East countries (Egypt, Sudan, Somalia, Libya, Morocco, United Arab Emirates, Jordan, Saudi Arabia, Yemen, Iraq, and Palestine)
3. **Time:** From August 2025 to December 2025
4. **Population:** Arabic Medical students and interns in the MEAN region

5. Inclusion Criteria

- Medical students and interns studying medicine in the Middle East countries
- Have access to online platforms

6. Exclusion Criteria

- Students or interns who refused to participate

7. Sampling

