We calculated the total sample size using Epi Info version 7.2.60(Epi InfoTM | CDC, n.d.) Assuming a 28.4% (Essa et al., 2024) prevalence rate and a 5% error margin with a 95% confidence interval, the sample size required for each country is 312. After adding a 10% nonresponse rate, the final sample size is about 343 for each country, so the total sample size will be 3773

8. Sampling Technique: Convenience Sampling

Operational design

1. **Pilot:** We will perform a pilot study in each country before starting the study to assess the readiness of the questions and the reliability of the questions via the Cronbach's alpha test.
2. **Study field:** an online questionnaire will be shared via an online platform with the target population.

3. Data collection method

An online questionnaire will be shared via social media platforms, including Facebook, WhatsApp, and Telegram.

The questionnaire consists of 6 sections

- The first section discusses the importance of the study for the participants, informing them that their data will be used only for research purposes, and obtaining informed consent
- The second section asks about the sociodemographic data and associated risk factors such as age, sex, residency, GPA, smoking, BMI, and eating habits
- The third section contains the GERDQ questionnaire(Jones et al., 2009). It is composed of 6 Likert scale questions that ask about GERD symptoms such as heartburn, nausea, and regurgitation. Each question has 4 answers scored from 0 to 3, making a rank from 0 to 18. If the participant scores 8 or more, this diagnoses GERD. Furthermore, the symptoms severity can be assessed. A score of 0-2 makes 0 % of having GERD, 3-7 makes a 50% likelihood of having GERD, 8-10 makes a 79% and 11-18 makes a 89% of having GERD. This questionnaire has a sensitivity being 65% and a specificity being 71% to diagnose GERD
- The Fourth section asks about the quality of life for GERD patients. We used the GERD-HRQL(Velanovich, 2007). This is a 16 Likert scale questionnaire that asks about the effect of GERD symptoms on the quality of life. The first 15 questions had 6 answers, ranging from no symptoms to Symptoms that are incapacitating – unable to do daily activities. This score ranges from 0 to 75. The sixteenth question asks about the present condition. The quality of life is calculated via the first 15 questions (scores from 0 to 75), with higher scores indicating lower quality of life.

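### GERD prevalence may be biased by topic-related self-selection into a social-media convenience sample, and the plan neither limits nor assesses this

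*Combined protocol and SAP*

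**What the plan says.** The first objective is "To assess the prevalence of GERD among medical students and interns in the Middle East". The protocol title begins "Prevalence of Gastroesophageal Reflux Disease, Its Association With Eating Behavior and Psychological Disturbance" and goes on to quality of life.

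Methodology gives "Sampling Technique: Convenience Sampling". Operational design, item 3 (Data collection method) adds: "An online questionnaire will be shared via social media platforms, including Facebook, WhatsApp, and Telegram". On the opening screen, "The first section discusses the importance of the study for the participants, informing them that their data will be used only for research purposes", and consent is obtained there. Sociodemographic items follow, then GerdQ, GERD-HRQL, DEBQ and DASS-21.

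The only exclusion criterion is "Students or interns who refused to participate". No count or description of these students is planned. The Sampling section allows for nonresponse by enlarging the sample: "After adding a 10% nonresponse rate, the final sample size is about 343 for each country, so the total sample size will be 3773". Under Statistical analysis, categorical data, which would include GERD status, are reported as a frequency and a percentage. No weighting, responder comparison or sensitivity analysis is described.

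**The concern.** The topic of the study and the outcome of objective 1 are the same condition. Students choose whether to take part after reading some description of the study. A student with heartburn may have more reason to open and finish a reflux questionnaire than one without. If so, the sample holds too many cases and the prevalence figure is too high.

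This bias differs from sampling error. The 5-point margin and the 10% addition deal with the number of responders, not with which students respond. More responders only narrow the interval around a shifted value. If promotion of the link differs between countries, the shift could differ too, and so could comparisons between countries. If distress about symptoms also drives response, the association between GERD and stress in objective 5 could be affected. Both of these further effects are conditional, and the documents give no figures for either.

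**Working it through.** **Inputs from the documents.** Planning prevalence 28.4%, margin 5 points, 95% confidence, 312 per country, 343 after the nonresponse addition, 3773 in total (Sampling). Eleven countries (Setting). A lower Egyptian prevalence of 17.1% (Rationale). GerdQ sensitivity 65% and specificity 71% (Data collection method).

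**Assumed input.** r is the participation rate of GerdQ-positive students divided by that of GerdQ-negative students. The documents give no value, so a range is shown on both sides of 1.

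**Step 1: the plan's own figures.** The plan states "prevalence rate and a 5% error margin with a 95% confidence interval, the sample size required for each country is 312".
- n = 1.96² × 0.284 × 0.716 / 0.05² = 312.5, against the stated 312.
- 312 × 1.10 = 343.2, stated as 343.
- 343 × 11 = 3773.

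The figures reproduce. They allow for random error only.

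**Step 2: shift under self-selection.** Observed prevalence = r·p / (r·p + 1 − p), with p = 0.284.

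| r | Calculation | Observed | Shift (points) |
|---|---|---|---|
| 0.8 | 0.2272 / 0.9432 | 24.1% | −4.3 |
| 1.0 | 0.284 / 1 | 28.4% | 0 |
| 1.1 | 0.3124 / 1.0284 | 30.4% | +2.0 |
| 1.25 | 0.355 / 1.071 | 33.1% | +4.7 |
| 1.5 | 0.426 / 1.142 | 37.3% | +8.9 |

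**Step 3: the r that uses up the margin.** Selection multiplies the odds by r, so r is the ratio of observed to true odds.
- True 28.4%, observed 33.4%: (0.334/0.666) / (0.284/0.716) = 1.26.
- True 17.1%, observed 22.1%: (0.221/0.779) / (0.171/0.829) = 1.38.

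**Step 4: coverage of the nominal 95% interval** (normal approximation, simple random sampling, true value 28.4%).
- With 312 responders in a country, coverage is about 57% at r = 1.25 and about 10% at r = 1.5.
- With 11 × 312 = 3432 pooled, the half-width is about 1.5 points. Even r = 1.1, a shift of 2.0 points, leaves coverage of about 29%.

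**Step 5: selection on true disease instead.** Take 28.4% as the true disease prevalence and apply the protocol's sensitivity and specificity.
- No selection: 0.284 × 0.65 + 0.716 × 0.29 = 39.2% GerdQ-positive.
- r = 1.25 on true disease raises the diseased share to 33.1%. Then 0.3315 × 0.65 + 0.6685 × 0.29 = 40.9%.

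The shift in the reported percentage is +1.7 points, against +4.7 in Step 2. The larger figures therefore need selection on the GerdQ result itself, that is, on the symptoms it scores.

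**The case against.** The strongest reply is that the participant-facing text is not in the documents. The sentence on the opening screen does not name GERD. The title is the protocol's, nothing shows that students will see it, and it also names eating behaviour, psychological disturbance and quality of life. This stands. The missing text cannot be counted as a gap, and a reader who infers that the survey is introduced around GERD goes beyond the documents. Even so, informed consent has to say what the study is about, and the plan does not ask for a neutral description.

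A reader might also infer that the link is open to all. The text says only that the questionnaire is shared on social media with the target population, which could mean closed class groups. Self-selection can occur in either setting.

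A third inference is that the sample will be enriched and the estimate too high. There are no participation data by symptom status. Upward bias is more plausible, but r = 0.8 would pull the estimate down by 4.3 points.

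The size also depends on the assumptions. The break-even r rises from 1.26 to 1.38 if the true figure is 17.1%, and the shift is well under half as large if selection acts on true disease. This stands too, and it is why a range is given and not one figure.

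Finally, a declared convenience sample already carries a general limit on inference. That is true, but topic-related selection is a part of that limit that can be reduced at almost no cost before the link goes out.

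**Conclusion.** The concern holds as a risk that the plan neither limits nor assesses. It is not a demonstrated bias. Objective 1 rests on voluntary entry to a study whose title leads with the outcome, and the prevalence is to be reported as a plain percentage.

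Under selection on GerdQ status, with a true 28.4%, values of r from 0.8 to 1.5 give observed prevalences from 24.1% to 37.3%. An r of about 1.26 (about 1.38 at 17.1%) equals the planned margin. These figures rest on an assumed r, on the planning prevalence being the true one, and on selection by the GerdQ result. The documents do not establish that the sample will be enriched, by how much, or that participants will see a reflux-centred invitation. The case for change is that a small rewording addresses a bias that more responders cannot remove and that is hard to repair after data collection.

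**What to change.** In Operational design, item 3:

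1. Specify a neutral heading and post text for the link and first screen, the same in all countries. An example is *Health, eating and wellbeing of medical students: whether or not you have any symptoms*. Disclose reflux in the consent text as one of several topics.
2. Keep GerdQ in its present early position. Moving DEBQ and DASS-21 ahead of it would put 33 + 21 = 54 items before a six-item outcome, and drop-out along the way could itself depend on symptoms.
3. Add one item, after GerdQ, asking whether having or not having symptoms influenced the decision to take part. Report it descriptively by country and GerdQ status. It reaches only those who take part, so it does not measure the bias.
4. Do not use that item to exclude responders, because exclusion removes mainly cases. With no enrichment, if an assumed 30% of cases and no others say yes, a true 28.4% becomes 0.1988 / (0.1988 + 0.716) = 21.7%.

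In Statistical analysis, report prevalence with a sensitivity table over r below and above 1, using true = observed / (observed + r × (1 − observed)). For example, an observed 28.4% would correspond to 33.1% at r = 0.8, 26.5% at 1.1, 24.1% at 1.25 and 20.9% at 1.5. State that r is assumed.

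The cost is minor rewording of the invitation before ethics approval, which the protocol still describes as to come, plus one extra item and a more cautious prevalence statement.

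### A GerdQ score of 8 or more is called a GERD diagnosis, so objective 1 would report a screen-positive share as the prevalence of GERD

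*Combined protocol and SAP*

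**What the plan says.** Objective 1 is the prevalence of GERD among medical students and interns. The only case definition is in Operational design, Data collection method, third questionnaire section: "If the participant scores 8 or more, this diagnoses GERD". That item goes on to offer a severity use, "Furthermore, the symptoms severity can be assessed", and supports it with likelihoods of disease: "A score of 0-2 makes 0 % of having GERD, 3-7 makes a 50% likelihood of having GERD", then "8-10 makes a 79% and 11-18 makes a 89% of having GERD". It ends with accuracy figures: "This questionnaire has a sensitivity being 65% and a specificity being 71% to diagnose GERD".

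Under Technical design, Sampling, the sample size assumes a 28.4% "prevalence rate and a 5% error margin with a 95% confidence interval, the sample size required for each country is 312". Recruitment is by "Sampling Technique: Convenience Sampling".

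The Statistical analysis section summarises categorical data by frequency and percentage. It plans chi-square and Mann-Whitney tests across sociodemographic groups. It then lists GERD with the continuous measures to be correlated and closes with multiple linear regression. The documents contain no confirmatory assessment, no allowance for misclassification and no label such as probable or screen-positive GERD.

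**The concern.** One item asserts a diagnosis and also states error rates that rule out treating the score as one. If the plan is followed, the percentage scoring 8 or more becomes the headline prevalence. By the plan's own sensitivity and specificity, that percentage and the prevalence of GERD can differ by more than 10 points. The 5-point margin behind the sample size would then be read as precision for GERD prevalence, when it is precision for an observed proportion.

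Two further problems come from the same item. The bands are introduced as severity but are likelihoods of having GERD. The item also gives a 50% likelihood at scores 3 to 7, which sits badly with counting everyone below 8 as free of disease.

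Any comparison that uses the cutoff inherits misclassification bias: towards the null if the error is non-differential, in either direction if it is not. Differential error is plausible, because distress may change symptom reporting and the quality-of-life instrument also concerns reflux symptoms ("This is a 16 Likert scale questionnaire that asks about the effect of GERD symptoms on the quality of life").

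**Working it through.** **Inputs.** Sensitivity Se = 0.65, specificity Sp = 0.71 and cutoff 8 (Data collection method, third questionnaire section). Planning prevalence 28.4%, margin 5 points, 95% confidence, 312 per country (Sampling). Eleven countries (Setting). *Assumption:* 65%/71% refers to the cutoff of 8. The plan attaches the figures to the questionnaire as a whole, but 8 is the only diagnostic cutoff it gives.

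**1. The plan's own figure.** n = 1.96² × 0.284 × 0.716 / 0.05² = 312.5, which matches the stated 312. Then 312 × 1.10 = 343.2, and 343 × 11 = 3,773. The calculation is sound for an observed proportion and makes no allowance for test error.

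**2. Expected raw share.** Raw = p × Se + (1 − p) × (1 − Sp).
- p = 0: 29.0%.
- p = 28.4%: 0.1846 + 0.2076 = 39.2%, which is 10.8 points above the truth.
- At the ends of the Middle East range in the Introduction, taken as true values: 8.7% appears as 32.1%, and 33.1% as 40.9%.

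**3. Where raw and true agree.** p = (1 − Sp) / [(1 − Sp) + (1 − Se)] = 0.29 / 0.64 = 45.3%. Below this the raw share is too high; above it, too low.

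**4. Predictive value at a true 28.4%.** PPV = 0.1846 / 0.3922 = 47.1%.

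**5. Do the bands fit 65%/71%?** With 79% and 89% in the two bands at or above 8, overall PPV must lie between 79% and 89%. PPV of at least 79% requires p of at least 62.7%. With 0% and 50% in the two bands below 8, at most half of the negatives can have GERD: 0.35p ≤ 0.71(1 − p), so p ≤ 0.71 / 1.06 = 67.0%. At p = 67.0%, PPV is 82.0%, inside the range. The two sets of figures therefore fit together only at a prevalence of about 63% to 67%.

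**6. Precision after correction.** Rogan-Gladen estimate = (raw + Sp − 1) / (Se + Sp − 1), with denominator 0.36. At a raw 39.2%:
- n = 312: half-width 5.4 points raw, and 5.4 / 0.36 = 15.0 points corrected.
- n = 11 × 312 = 3,432 pooled: 1.63 points raw, 4.5 points corrected.

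These treat Se and Sp as known and assume simple random sampling, which convenience sampling does not provide, so they are nominal.

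**7. Reading a negative corrected estimate.** If 28.4% were the observed share at n = 312, the correction gives (0.284 − 0.29) / 0.36 = −1.7%. The half-width is 5.0 / 0.36 = 13.9 points, so the interval runs from about −15.6% to 12.2%. It includes plausible positive prevalences, so a negative point estimate alone does not refute the scenario.

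**8. Group comparisons on the cutoff.** With non-differential error, differences in GERD prevalence between groups shrink by the factor Se + Sp − 1 = 0.36.

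**The case against.** The strongest reply is that the size and even the direction of the error are not established. The 39.2% and 47% need 28.4% to be a true prevalence, but the Rationale gives it only as what an earlier survey reported, with no instrument named. They also need 65%/71% to hold in students, for whom the plan gives no accuracy figures; the title of the cited tool paper refers to primary care. The same item's 79% and 89% would imply a much higher PPV than 47%. With other accuracy pairs, taken purely as illustrations, a raw 39.2% corrects to 39.3% (55%/71%) or 42.7% (65%/80%), which is not below the raw share. All of this stands, and it limits the numbers to conditional illustrations. It does not rescue the diagnostic claim: if the applicable accuracy is unknown, there is less reason to call the score a diagnosis.

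A second reply is that the plan never writes out a prevalence estimator, so reporting the raw share is an inference. That is true, but no other estimator or label appears anywhere in the documents.

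A third is that the correlations and linear regression may use the continuous score, where this cutoff misclassification does not arise. That also stands. The plan does not say which form each analysis uses. It names no comparison of quality of life by GerdQ status, so no specific bias can be assigned to objective 2.

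**Conclusion.** The point holds as a problem of label and estimand. As written, objective 1 would present a screen-positive share as GERD prevalence. If 65%/71% applies to the cutoff and to students, the raw share cannot be expected to fall below 29% and is too high for any true prevalence under 45.3%, which includes every prevalence the plan cites if those are taken as true values. At a true 28.4% the gap is 10.8 points. Separately, and whatever the true prevalence in students, the bands and the 65%/71% agree only at a prevalence of about 63% to 67%, so they cannot both describe a population near 28.4%.

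Three stronger conclusions are tempting but unsupported:
- A reader might infer that the study will overstate GERD by about 11 points and that most positives will be false. That depends on a true prevalence and an accuracy in students that the documents do not establish.
- A reader might infer that 312 per country is wrong. It is correct for the observed proportion, and no larger sample is called for if that proportion is the estimand.
- A reader might infer that the earlier student surveys (17.1% to 28.4%), lying below the 29% floor, disprove 65%/71%. The documents do not say how those surveys measured GERD.

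**What to change.** 1. Replace the diagnostic wording with *screens positive for probable GERD*. Use that label wherever the share scoring 8 or more is reported, including the title and objectives 1, 4 and 5.
2. State the estimand: *The objective 1 estimand is the proportion of respondents with a GerdQ score of 8 or more. The 5-point planning margin (312 per country) refers to this proportion and not to the prevalence of GERD.*
3. Prespecify one secondary Rogan-Gladen corrected prevalence with a 95% CI, pooled (per country optional), at 65%/71% and at a few other sensitivity/specificity pairs that the sponsor justifies. Truncate negative point estimates at 0. Call a scenario incompatible with the data only if its whole interval lies below 0.
4. Reconcile the 0/50/79/89% bands with 65%/71%, and do not use the bands as severity grades.
5. For each analysis, say whether it uses the GerdQ score or the cutoff. For cutoff-based comparisons, note that misclassification biases the result towards the null if non-differential and in either direction otherwise.

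The cost is wording plus one short secondary table, with no new data and no larger sample. The headline becomes more modest and the corrected interval is wide: nominally about ±4.5 points pooled and ±15 points per country in the 28.4% example. The raw share is still reported.

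### A GERDQ score of 8 or more is the only case rule and no question on diagnosis or reflux medicine is described, so known cases scoring below 8 on treatment count as GERD-free

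*Combined protocol and SAP*

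**What the plan says.** The Introduction describes GERD in these terms: "It is a chronic condition that is characterized by the regurgitation of stomach contents into the esophagus and is associated with heartburn". Objectives, item 1, is "To assess the prevalence of GERD among medical students and interns in the Middle East".

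Under Operational design, Data collection method, the third questionnaire section is the GERDQ: "It is composed of 6 Likert scale questions that ask about GERD symptoms such as heartburn, nausea, and regurgitation". Each item scores 0 to 3, and the only classification rule is "If the participant scores 8 or more, this diagnoses GERD". The same paragraph states: "This questionnaire has a sensitivity being 65% and a specificity being 71% to diagnose GERD".

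The second questionnaire section collects "associated risk factors such as age, sex, residency, GPA, smoking, BMI, and eating habits". Neither this list nor any other part of the document mentions a previous GERD diagnosis, reflux medicine, or a rule for participants under treatment. The only exclusion criterion is "Students or interns who refused to participate", so treated students are eligible.

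Statistical analysis lists Chi-square and Mann-Whitney U tests, correlations among the GERD, GERD-HRQL, DEBQ and DASS-21 scores, and a multiple linear regression. It does not define a GERD versus no-GERD comparison.

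**The concern.** The objective is the prevalence of a condition that the protocol calls chronic, but the case rule looks only at a score built from items described as asking about symptoms. A student who has been diagnosed, takes medicine and scores below 8 is a case under the chronic-disease reading and a non-case under the rule.

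Two things are at stake. For objective 1, the reader cannot tell whether the reported figure means current symptomatic GERD or all GERD, including treated disease. For objectives 2 to 5, such students carry a low GERD score together with their own quality-of-life, eating-behaviour, BMI and DASS-21 values, whether the score is used as a continuous variable or split at 8.

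Because neither diagnosis nor treatment is described as being recorded, the data as planned could not show afterwards how large this group was.

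**Working it through.** **Inputs from the protocol.** Assumed prevalence p = 28.4%, margin 5 points, 95% confidence (Sampling). Sensitivity Se = 65% and specificity Sp = 71% (Data collection method, third section).

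**Assumed input.** c is the share of true cases that are treated and controlled. The documents do not give it, so 10%, 20% and 30% are shown.

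**Step 1: the plan's own figure.** n = 1.96² × 0.284 × 0.716 / 0.05² = 312.5, against 312 stated. Then 312 × 1.10 = 343.2, against 343, and 343 × 11 countries = 3773. The sample size reproduces and is not in dispute.

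**Step 2: what the rule measures with no controlled cases.** Measured prevalence = Se × p + (1 − Sp) × (1 − p) = 0.65 × 0.284 + 0.29 × 0.716 = 0.1846 + 0.2076 = 39.2%. This is 10.8 points above the true 28.4%.

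**Step 3: add controlled cases.** If they never score 8 or more, the loss is c × p × Se = c × 18.46 points. If they score 8 or more at the false-positive rate of 29%, the loss is c × p × (0.65 − 0.29) = c × 10.22 points.

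| c | Never 8 or more: measured (loss) | At 29%: measured (loss) |
|---|---|---|
| 10% | 37.4% (1.8) | 38.2% (1.0) |
| 20% | 35.5% (3.7) | 37.2% (2.0) |
| 30% | 33.7% (5.5) | 36.2% (3.1) |

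Every entry is still above 28.4%. In the first column, the net error turns downward only when c exceeds 10.82 / 18.46 = about 59%.

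**Step 4: true cases among those scoring below 8.** With c = 0: 0.35 × 0.284 / (1 − 0.3922) = 16.4%. With c = 20%, none scoring 8 or more: (0.284 × 0.80 × 0.35 + 0.284 × 0.20) / (1 − 0.3553) = 0.1363 / 0.6447 = 21.1%. Over c = 10% to 30% the share is 18.8% to 23.3%, or 17.7% to 20.4% if controlled cases score 8 or more at the 29% rate.

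**Step 5: what a combined rule would read.** Counting a score of 8 or more, or diagnosed and on treatment, with c = 20% and all controlled cases captured: 35.5% + 5.7% = 41.2%. The combined figure recovers the treated cases but leaves the false positives in place.

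**The case against.** **Net direction.** A reader might infer that the study will understate GERD prevalence. The protocol's own figures do not support that. The stated specificity pushes the estimate up by more than controlled cases pull it down over the whole range shown. What remains is a loss relative to a definition that includes treated cases.

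**Size.** A reader might also take the loss as c × 28.4, that is 2.8, 5.7 or 8.5 points, and conclude that a treated share of 17.6% uses up the whole 5-point margin. That assumes every controlled case would otherwise have scored 8 or more, which contradicts the stated 65% sensitivity.

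**Overlap with the quoted sensitivity.** The protocol does not say who was in the sample behind the 65%. If treated patients were included, part of this loss is already in that figure. If they were not, correcting for sensitivity and specificity would not remove it: at c = 20%, with controlled cases at the false-positive rate, the corrected value is (0.3718 − 0.29) / 0.36 = 22.7%, not 28.4%. The documents do not settle which applies.

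**Unseen content.** The six items are not all listed, no recall window is given, and the risk-factor list is open-ended. How often treated students score below 8 is therefore unknown, and a treatment question might exist. Even so, the stated rule would not use the answer.

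**Associations.** No two-group comparison is defined, and attenuation towards the null would require treatment to be unrelated to the exposures, which is not shown. Nor do the documents support a claim that countries with easier access to acid suppressants would appear to have less GERD; comparing countries is not an objective.

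**Target.** The Introduction also characterises GERD by its symptoms, so a symptom-based prevalence is a legitimate target. That stands, but the plan should then label it so.

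**Conclusion.** The point holds in a limited form. The case rule counts a known, treated case scoring below 8 as GERD-free, and the plan describes nothing that would identify such a student. For assumed controlled shares of 10% to 30%, this lowers the measured figure by 1.8 to 5.5 points if controlled cases never reach 8, or by 1.0 to 3.1 points if they reach it at the false-positive rate.

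These sizes assume a true prevalence of 28.4% that includes treated cases, and that the quoted sensitivity applies to cases not controlled on treatment. If the quoted sensitivity already reflects treated patients, the loss is smaller.

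The net prevalence error is not shown to be downward. The bias in the association analyses can go either way, depending on whether treatment is related to eating behaviour, BMI or psychological scores. This is a misclassification that can be reduced cheaply and could not be sized later from the planned data; it does not invalidate the design.

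**What to change.** 1. Add two closed questions to the second questionnaire section: whether a doctor has ever diagnosed GERD, and whether acid-reducing medicine was taken for reflux during the questionnaire's recall period. State that period in the protocol.
2. Label a GERDQ score of 8 or more as current symptomatic GERD. Beside it, report the share diagnosed and on treatment with a score below 8, and the combined figure. Note that the combined figure does not correct false positives.
3. For objectives 2 to 5, add a sensitivity analysis that omits diagnosed, treated students scoring below 8, or analyses them as a third group.

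The cost is a slightly longer form and some extra table rows, with no additional participants or procedures. The downside is that diagnosis and medicine use are self-reported.
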